### 8.2.2 Imputation of adverse event start dates

To assess if AEs are treatment emergent, missing onset dates will be imputed according to the following rules:

- If day is missing and month and year of AE onset is the same as the month and year of first dose of study treatment (or date of randomization for patients on standard of care), then the onset date of the AE will be assumed to be the same as the date of first dose of study treatment (or date of randomization for patients on standard of care).
- If day and month is missing and year of AE onset is the same as year of first dose, then the date of onset will be assumed to be the same as the first dose of study treatment (or date of randomization for patients on standard of care).
- Otherwise, if day is missing, then use YYYY-MM-01, and if day and month are missing, then use YYYY-JAN-01.
- Completely missing onset dates will not be imputed. AEs with a completely missing onset date will be considered treatment-emergent.

### 8.2.3 Imputation of previous/concomitant medication start/stop dates

To assess if medications are prior or concomitant, missing onset dates will be imputed according to the following rules:

- If day is missing and month and year are both available, use 01 of the month or the date of first dose of study treatment (or date of randomization for patients on standard of care) whichever is later.

- If only the year is available, use 01 Jan of the year or the date of first dose whichever is later.
- Completely missing onset dates will not be imputed.

Likewise, to assess if a medication is prior, missing stop dates will be imputed according to

- If the day is missing: Assume the last day of the month.
- If the month is missing: Assume 31 Dec of the year.

Completely missing stop dates will not be imputed.

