## **11 Prior and concomitant medication**

All prior and concomitant medication will be coded using the latest version of World Health Organization drug dictionary (WHO Drug).

The preferred term grouped by ATC level 4 will be used for presentation and sorted in descending order of frequency in total (the treatment groups together) at the top in the table. Prior medication, concomitant medication at randomization and onset of new concomitant medication after randomization during the study will be summarized separately.

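### The SAP moves every partial medication start date from an earlier month or year to the first-dose date, contradicting the record and possibly blurring the descriptive medication tables

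*SAP*

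**What the plan says.** SAP 8.2.3 gives its purpose as follows: "To assess if medications are prior or concomitant, missing onset dates will be imputed according to the following rules". Two bullets deal with partial starts.

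- Day missing: "If day is missing and month and year are both available, use 01 of the month or the date of first dose of study treatment", with the randomization date standing in for first dose in the standard-of-care arm, and the later of the two dates taken.
- Month and day missing: "If only the year is available, use 01 Jan of the year or the date of first dose whichever is later". This bullet names no substitute for standard of care.

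A stop date with a missing day goes to the end of its month, and one with a missing month goes to 31 Dec. Nothing compares the imputed start with the stop.

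SAP 8.2.2, on adverse event onset, is built differently. Its first rule is conditional: "If day is missing and month and year of AE onset is the same as the month and year of first dose of study treatment", the onset is set to that date; in the standard-of-care arm, randomization takes its place. A parallel rule covers the same year. For the rest: "Otherwise, if day is missing, then use YYYY-MM-01, and if day and month are missing, then use YYYY-JAN-01".

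SAP 11 uses the medication classification. Prior medication and medication in use at randomization each get a summary, and "onset of new concomitant medication after randomization during the study will be summarized separately".

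**The concern.** A partial date still carries information. If the record says 2015, the drug started years before the trial, and only the exact day is in doubt. Imputation should fill in what is unknown and keep what is known. Taking the later date is reasonable when the recorded period contains the first dose, because the order of the two events is then ambiguous. Outside that case it replaces a known earlier period with Day 1.

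What is at stake is how background therapy is described. The trial is open-label, Protocol 5.4.7.2 leaves most concomitant therapy unrestricted, and Protocol 5.4.4.3 states that glucocorticoids could affect biomarkers and possibly clinical outcome. Readers will use the SAP 11 tables to see what patients were taking before randomization and what was added afterwards. With 18 patients per arm, a few misdated records could visibly change a row.

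**Working it through.** The plan gives no figure to reproduce, so the check applies both date rules as written.

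**Inputs.** *R* is the reference date: first dose, or randomization for standard of care where the rule says so. *F* is the first day of the recorded month, or 01 Jan of the recorded year. The documents give no patient dates, so any value of *R* below is an assumption.

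**Formulas.**

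- Medication start (SAP 8.2.3): S = max(F, R).
- Adverse event onset (SAP 8.2.2): S = R if the recorded period is the period of R; otherwise S = F.

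**General result.** If the recorded month or year ended before R, then F < R and max(F, R) = R. This holds for every R, so the result does not depend on the assumed date.

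**Examples, assuming R = 15 Jul 2020.**

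| Recorded start | Medication rule (8.2.3) | Adverse event logic (8.2.2) |
|---|---|---|
| 2015 | 15 Jul 2020 | 01 Jan 2015 |
| 2019 | 15 Jul 2020 | 01 Jan 2019 |
| Mar 2015 | 15 Jul 2020 | 01 Mar 2015 |
| Jun 2020 | 15 Jul 2020 | 01 Jun 2020 |
| Jul 2020 | 15 Jul 2020 | 15 Jul 2020 |
| 2020 | 15 Jul 2020 | 15 Jul 2020 |
| Aug 2020 | 01 Aug 2020 | 01 Aug 2020 |

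The rules agree when the recorded period contains R or lies after it. They differ only for earlier periods.

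**Count of possible values.** Jan 2010 to Jun 2020 has 10 × 12 + 6 = 126 month-year values. The medication rule moves 126 of 126 to Day 1; the adverse event logic moves 0 of 126. For the years 2010 to 2019 the counts are 10 of 10 and 0 of 10. These are counts of possible date values, not of records in the trial.

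**Start after stop.** Assume R = 10 Apr 2020, a recorded start of Feb 2020 and a stop on 15 Mar 2020. Then S = max(01 Feb 2020, 10 Apr 2020) = 10 Apr 2020, which is 16 + 10 = 26 days after the stop.

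**Where the record lands in SAP 11.** There are four cases for an earlier partial start.

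1. Stopped before R: it can still be classed as prior by its stop date, although its imputed start is later than that stop.
2. Ongoing, with R on the day of randomization: S equals the randomization date. The SAP does not say whether that counts as in use at randomization or as new onset.
3. Ongoing, active arm, with R after the day of randomization: S is later than randomization, so read literally the drug is new onset. A standard-of-care record with only the day missing cannot fall here, because its R is the randomization date.
4. Standard of care, year only: the bullet names only first dose, and this arm receives no study drug, so R is undefined.

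**The case against.** The strongest reply is that the wrong date need not produce a wrong table. SAP 8.2.3 imputes stop dates in order to identify prior medication, so a stopped drug can be sorted correctly whatever its imputed start. Protocol 5.5.1.3 places randomization and first dose at the same visit, so for an ongoing drug the imputed start will normally be the day of randomization. The natural home for it is then the table of medication in use at randomization, which is right. SAP 11 plans summaries by preferred term, with no analysis of start day or duration, so a start later than a stop has no shown effect on a result. Prior medication is also collected at screening (Protocol 5.5.2.3), and the case report form, which is not available here, may already keep the categories apart.

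Most of this stands. A reader might infer that long-standing drugs are certain to move into the wrong table, or that the 126 of 126 count measures the harm. The documents support neither: the count describes the rule, and the table depends on conventions that the SAP leaves open. Nor do they support a link to efficacy. The primary Fisher test uses no medication dates, the exact logistic sensitivity analysis uses the stratification factor, and no subgroup analysis is planned (SAP 12.1 and 12.3).

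The reply does not rescue the rule itself. Correct sorting would rest on an unstated convention for Day 1 starts and on first dose never falling after the day of randomization. No other text in either document limits the rule to the period of first dose.

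**Conclusion.** The rule is wrong as written, and the consequence is small. It is certain that every partial start from a month or year before that of first dose is imputed to the first-dose date, against the record, and that a start after a recorded stop can result. It is possible, but not certain, that long-standing drugs move from prior or in use at randomization to new onset in SAP 11. That would happen if Day 1 starts are coded as new, or if an active-arm first dose is dated after randomization. In the second case the active arms could be handled differently from standard of care. The year-only bullet is undefined for standard of care in any event.

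The number of affected records cannot be known from the documents. Only descriptive medication summaries are exposed; no efficacy conclusion changes. The date result rests on no assumption beyond reading the text literally.

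**What to change.** Reword both start-date bullets in SAP 8.2.3. Use the first-dose date, or the randomization date for standard of care in both bullets, only when two conditions hold: the recorded month and year (or the year, if that is all there is) equal those of that reference date, and the stop date does not precede it. Otherwise use the first day of the recorded month, or 01 Jan of the recorded year. That fallback is the one already in SAP 8.2.2; the stop-date check is new.

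The cost is about two lines of SAP text and the matching change in the derivation program. No additional data are needed and the efficacy analyses are untouched.

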### **8.3 Multicenter studies**

No effects of centers will be evaluated in this study due to the small numbers at individual sites.

### **8.4 Multiple comparisons and multiplicity**

There will be no adjustments for multiplicity for the two pairwise treatment comparisons for the primary endpoint. Multiplicity for the sequential comparisons at the end of Stage 1 and at the end of Stage 2 are however accounted for by the design.

### **8.5 Derived and computed variables**

#### **8.5.1 Treatment success**

Treatment success is achieved for patients not requiring IMV or ECMO by Day 15. If IMV or ECMO is required at any visits prior to Day 15/date of early discontinuation, but no longer required at Day 15/date of early discontinuation, treatment success has been achieved. If IMV or ECMO is not initiated during the study, treatment success has been achieved. As stated in Section 8.2.1, patients who discontinue study treatment (or discontinue the study if randomized to standard of care) prior to Day 15 and had ECMO or IMV on their last assessment by the time of study treatment discontinuation, will be considered not having achieved treatment success by Day 15. Patients who discontinue prior to Day 15 without ever having initiated IMV/ECMO, have achieved treatment success by Day 15. Patients discontinuing prior to Day 15 due to having significantly improved will be considered having achieved treatment success. Patients who died by Day 15, have not achieved treatment success regardless of IMV/ECMO use by Day 15.

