3.1 Background

This protocol has been prepared in response to the request formulated by [name] (current President of the Italian Consiglio Superiore di Sanità and member of the Scientific Committee of the Italian Civil Protection, previously serving as Principal Investigator for the European development of emapalumab in children with primary HLH), and the Scientific Director of the National Institute for Infectious Diseases (INMI) Lazzaro Spallanzani, [name]. INMI is the only IRCCS (national institute for research and care of the Italian Ministry of Health) fully devoted to Infectious disease and as WHO-CC for diagnosis, research, care and training against highly infectious diseases. Both are members of the Scientific Committee of the Italian Civil Protection and are working in strict collaboration with the Italian national competent authority (AIFA) and are committed to investigate, among others, the use of emapalumab and anakinra, in patients suffering from the SARS-CoV-2 infection and experiencing respiratory distress.

For the preparation of this protocol, expertize in hyperinflammation, in the treatment of cytokine release syndromes, and in the treatment of infection diseases, has been provided by [name], [name] and [name], together with contribution of the many physicians currently involved in the treatment of patients infected with SARS-CoV-2 in Italy.

Following discussions with the FDA and given the global urgency to develop treatment for patients with SARS-CoV-2 infection and experiencing respiratory distress, the study protocol has been amended to include US study sites and patients. The current study is intended to provide proof of concept for the treatment of anakinra and/or emapalumab as add-on to standard of care, and to guide the plan for further development.

The objective of this study is to investigate new possibilities to reduce the number of patients requiring mechanical ventilation. This is intended to address the most urgent need to preserve the access to intense care unit support to the lower possible number of patients and may potentially reduce mortality.

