4.1.1 Primary endpoint

The primary endpoint is treatment success, defined as not requiring any of the following by Day 15:

- Invasive mechanical ventilation or
- Extracorporeal membrane oxygenation (ECMO).

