5.5.1.5 Visit 6 (Day 15)

Please refer to Table 2 for the clinical and laboratory parameters to be collected during these visits. For study drug administration schedule, see Section5.4.5.

Effort should be made to adhere to the schedule of assessment. However, a visit window of ± 1 day will be allowed for Visit 6 (Day 15).

During the treatment period (Days 1 to 15), clinical and laboratory assessments and procedures should preferably be performed before IMP administration

The primary endpoint will be evaluated at Visit 6 (Day 15).

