7.3.8 Handling of missing data

There will be no imputation of missing data for the primary endpoint (treatment success by Day 15), but patients who discontinue study treatment (or discontinue the study if randomized to standard of care) prior to Day 15 and had IMV or ECMO on their last assessment by the time of study treatment discontinuation, will be considered not having achieved treatment success by Day 15. Patients discontinuing prior to Day 15 without ever having initiated IMV/ECMO, will be considered having achieved treatment success by Day 15. Patients discontinuing prior to Day 15 will be considered having achieved treatment success. Patients who died by Day 15, have not achieved treatment success regardless of IMV/ECMO use by Day 15.

For change-from-baseline efficacy endpoints at Day 15, the last observation carried forward (LOCF) approach will be used to impute missing data, using the last post-baseline observation available for each patient.

8 Data collection, handling and record keeping

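### The protocol does not say how IMV or ECMO that ended before Day 15 counts in the primary endpoint; SAP 8.5.1 counts it as success, and no sensitivity analysis uses the other reading

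*SAP*

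**What the plan says.** Protocol 4.1.1 reads: "The primary endpoint is treatment success, defined as not requiring any of the following by Day 15", followed by IMV and ECMO. SAP 3.4.1 uses the same wording. Protocol 3.1 gives the aim: "The objective of this study is to investigate new possibilities to reduce the number of patients requiring mechanical ventilation". Protocol 5.5.1.5 places the evaluation at Visit 6 and allows that visit one day either side of Day 15.

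SAP 8.5.1 adds a derivation rule. It begins "If IMV or ECMO is required at any visits prior to Day 15/date of early discontinuation, but no longer required at Day 15" (or at early discontinuation), and its conclusion is treatment success.

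Protocol 7.3.8 deals with discontinuers and deaths:
- It applies to "patients who discontinue study treatment (or discontinue the study if randomized to standard of care) prior to Day 15".
- Those who "had IMV or ECMO on their last assessment by the time of study treatment discontinuation" are failures.
- Those who never started support are successes, and deaths by Day 15 are failures.
- It also states, without condition: "Patients discontinuing prior to Day 15 will be considered having achieved treatment success". SAP 8.2.1 and 8.5.1 restrict that sentence to patients who stopped because of significant improvement.

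The one sensitivity analysis of the primary endpoint (Protocol 7.3.3.1.1, SAP 12.1) is an exact logistic regression that adjusts for glucocorticoid stratum. It keeps the same outcome variable.

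**The concern.** A patient ventilated on Day 5 and weaned by Day 12 did require ventilation. Counting that patient as a success sits poorly with the aim in Protocol 3.1. The headline wording permits that classification but does not state it, so a reader with only the protocol could derive a different primary result from the same data.

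The endpoint drives a binding futility rule at Stage 1 (SAP 5.1). Under Protocol 7.1 and SAP 6, a result significant at the 5% level at Stage 2 may be used to seek approval. Neither document says which definition the assumed 50% and 80% success rates refer to, so the stated power cannot be tied to either.

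**Working it through.** **1. Classification by document**

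| Patient | Protocol | SAP |
|---|---|---|
| Alive at Day 15, never on support | success | success |
| On support at Day 15 | failure | failure |
| Died by Day 15 | failure (7.3.8) | failure (8.2.1, 8.5.1) |
| Completer, support ended before Day 15 | not stated | success (8.5.1) |
| Discontinuer on support at last assessment | failure by one sentence of 7.3.8, success by the unconditional one | failure |
| Discontinuer, support already ended | covered only by the unconditional sentence | success (8.5.1) |

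Two further mismatches affect the same variable.
- **Trigger.** The discontinuer rule looks at treatment discontinuation in the active arms but at study discontinuation in the control arm. Under Protocol 5.3.3.1, patients who stop treatment stay in the study. An active patient who stops drug while off support and is ventilated afterwards can therefore be judged at the earlier date. A control patient with the same course is judged at Day 15.
- **Window.** Protocol 5.5.1.5 allows Visit 6 on Days 14 to 16. SAP Table 2 assigns Day 14 to Visit 5 and only Days 15 and 16 to Visit 6. This matters only for patients with earlier IMV or ECMO, because SAP 8.5.1 makes patients who never started support successes without a Visit 6 status.

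**2. The plan's own figure**

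Inputs from Protocol 7.1 and 7.3.6: 9 + 9 patients per arm, one-sided Fisher's exact test, futility if p > 0.690 and efficacy if p < 0.025 at Stage 1, efficacy if p < 0.159 at Stage 2, true success rates 50% and 80%. For x active and y control successes out of n per arm, with t = x + y:

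p = Σ(k ≥ x) C(n,k)·C(n,t−k) / C(2n,t)

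Exact enumeration gives efficacy at Stage 1 in 15.3% of trials and at Stage 2 in 58.3%, so power is 73.6%. The stated 74% reproduces.

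**3. Both readings applied to the same simulated patients**

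Per arm, let a be the probability of being alive and never on support, and w the probability of support that has ended with the patient alive and off support at Day 15. Success is a + w under the SAP rule (status) and a under the any-use reading. All other patients fail under both.

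The documents give no figure for w. It is assumed in three ways, with every any-use failure taken as ventilated and no early discontinuation:
- 50%/80% are any-use rates, and a fraction e of ventilated patients is weaned: w = e(1 − a). Example, e = 0.2: active 0.80 + 0.2 × 0.20 = 0.84; control 0.50 + 0.2 × 0.50 = 0.60.
- 50%/80% are status rates s: a = 1 − (1 − s)/(1 − e). Example, e = 0.1: active 1 − 0.20/0.90 = 0.778; control 1 − 0.50/0.90 = 0.444.
- 50%/80% are any-use rates, and the same number of percentage points is weaned in both arms.

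| 50%/80% are | Weaned | Power, any-use | Power, status | Opposite verdicts |
|---|---|---|---|---|
| any-use rates | 10% of ventilated, both arms | 73.6% | 67.2% | 11.0% |
| any-use rates | 20%, both arms | 73.6% | 60.1% | 19.2% |
| any-use rates | 30%, both arms | 73.6% | 52.4% | 26.9% |
| any-use rates | 30% active, 10% control | 73.6% | 76.7% | 12.7% |
| status rates | 5%, both arms | 76.7% | 73.6% | 6.1% |
| status rates | 10%, both arms | 79.9% | 73.6% | 10.4% |
| status rates | 20%, both arms | 86.4% | 73.6% | 16.8% |
| any-use rates | 5 points, both arms | 73.6% | 74.4% | 12% |
| any-use rates | 10 points, both arms | 73.6% | 76.3% | 18% |

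Starting instead from status rates and removing 5 to 15 points in both arms leaves any-use power at about 73.3%.

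**4. One patient at the Stage 2 boundary**

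14 vs 10 of 18 gives p = 0.1445 (efficacy). Reclassifying one control patient gives 14 vs 11, p = 0.2353. Reclassifying one active patient gives 13 vs 10, p = 0.2443. Neither is efficacy.

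**The case against.** The strongest reply is that the analysis rule is settled. SAP 8.5.1 says how ended support counts, and SAP 5.2 has the SAP locked and signed before Stage 1. The protocol also leans partly that way, since it evaluates at Visit 6 and fails discontinuers by their last assessment. This stands. A reader might infer that the primary analysis is undefined, or that the protocol clearly means any use and the SAP contradicts it. The documents support neither: the protocol wording is open, and the SAP closes it.

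The other reading is also not hidden. The time-to-IMV-or-ECMO analysis counts initiation, the swimmer plot in SAP 12.1 marks use at each visit, and the ordinal scale has its own IMV/ECMO category by visit. None is a substitute. The time-to-event analysis gives date of death as an example of a censoring date (SAP 8.5.2) and is not run at Stage 1 (SAP 12.2). The swimmer plot and the ordinal scale are descriptive.

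The sizes depend on assumed weaning. Equal fractions of ventilated patients reclassify more control than active patients, because 50% against 20% are ventilated; that drives the large power changes. With equal percentage points, power barely moves, although verdicts in individual trials still differ. The one-patient flips would follow from any misclassification at 18 per arm and say nothing specific about this definition.

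The sub-points are modest. The unconditional sentence looks like a dropped clause, and control patients have no study drug to stop, so some difference in trigger is unavoidable.

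**Conclusion.** The inconsistency between the protocol and the SAP is real and should be corrected. The protocol does not classify ended support in completers, the SAP counts it as success, and no sensitivity analysis of treatment success uses the any-use reading. Protocol 7.3.8 contradicts itself on discontinuers, and the arms are judged at different events.

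Under the weaning assumptions shown, the two readings give opposite efficacy verdicts in about 6% to 27% of trials. Power under the alternative reading is almost unchanged if equal percentage points are reclassified, and 52% to 86% against 73.6% if equal fractions of ventilated patients are weaned. Deaths without ventilation, or weaning rarer than assumed, would reduce the share of opposite verdicts.

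A reader might infer that the SAP rule favours the active drugs or that the stated power is wrong. Neither follows. The direction depends on the weaning pattern, and 74% reproduces at the stated rates. What is missing is which definition those rates describe.

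**What to change.** 1. State one definition in the same words in Protocol 4.1.1 and 7.3.8 and in SAP 3.4.1, 8.2.1 and 8.5.1. The choice is the sponsor's. In an open-label trial already under way, aligning the wording to SAP 8.5.1 is least disruptive.
2. Prespecify the other reading as a sensitivity analysis of treatment success at Stage 1 and Stage 2. If the SAP rule is kept, this means any IMV, any ECMO or death by Day 15 is failure.
3. In Protocol 7.3.8, replace the unconditional sentence with the SAP's qualified one, or delete it.
4. In every arm, use IMV/ECMO and survival data collected through Day 15, including after treatment is stopped. Apply the last-assessment rule only to patients who leave the study before Day 15 (for example under Protocol 5.4.7.2), and in the same way in every arm.
5. Reconcile the Day 14 window between Protocol 5.5.1.5 and SAP Table 2.
6. Record the end date of IMV/ECMO, or state that visit status is used. Protocol 5.5.3.1 names only the date and time of the requirement.
7. State in Protocol 7.1 and SAP 6 which definition the 50% and 80% rates refer to.

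The cost is a protocol amendment, matching SAP text and one more derived variable, plus an end-date field if that route is taken. Changing the SAP rule itself while open-label data accrue would risk appearing data-driven; if that route is chosen, it should be done before the SAP is locked for Stage 1, with the reason documented.
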